## Hematology

- Proportions of participants with mild, moderate, and severe results for any hematology parameter will be presented for participants who enrolled prior to Protocol v11.0 in **Table 124** by treatment group severity at baseline, time point, and maximum severity across all graded chemistry parameters. Proportions of participants with results that are mild, moderate, severe, life-threatening, or result in death for any hematology parameter will be presented for participants who enrolled under Protocol v11.0 in **Table 125** by treatment group, severity at baseline, time point, and maximum severity across all graded chemistry parameters.
- Proportions of participants with graded abnormal results will be presented by treatment group, severity at baseline, time point, and severity separately for participants enrolled prior to Protocol v11.0 and for participants enrolled under Protocol v11.0 for hematology parameters beginning in **Table 126** through **Table 137**. Hematology parameters with separate high and low toxicity ranges will be summarized by maximum severity with high and low ranges indicated. The proportions of participants with ONR results will be presented by treatment group, severity at baseline, time point, and severity for hematology parameters that do not have toxicity grading ranges defined in **Table 138** through **Table 145**.
- Proportions of participants with graded CS hematology results post-baseline will be presented by parameter, treatment group, and maximum severity of all CS results post-baseline for participants enrolled prior to Protocol v11.0 in **Table 156** and for participants enrolled under Protocol v11.0 in **Table 157**. The proportions of participants with CS ONR hematology results post-baseline will also be presented by parameter, treatment group, and maximum severity of all CS results for parameters that do not have toxicity grading ranges defined in **Table 158** for participants enrolled prior to Protocol v11.0 and in **Table 159** for participants enrolled under Protocol v11.0.

## Coagulation

- Proportions of participants with mild, moderate, and severe results for any coagulation parameter will be presented for participants who enrolled prior to Protocol v11.0 in **Table 160** by treatment group, severity at baseline, time point, and maximum severity across all graded chemistry parameters. Proportions of participants with results that are mild, moderate, severe, life-threatening, or result in death for any coagulation parameter will be presented for participants who enrolled under Protocol v11.0 in **Table 161** by treatment group, severity at baseline, time point, and maximum severity across all graded chemistry parameters.

- Proportions of participants with graded abnormal results will be presented by treatment group, severity at baseline, time point, and severity separately for participants enrolled prior to Protocol v11.0 and for participants enrolled under Protocol v11.0 for coagulation parameters beginning in **Table 162** through **Table 167**.
- Proportions of participants with graded clinically significant coagulation results post-baseline will be presented by parameter, treatment group, and maximum severity post-baseline for participants enrolled prior to Protocol v11.0 in **Table 171** and for participants enrolled under Protocol v11.0 in **Table 172**.

## Urinalysis

- Proportions of participants with mild, moderate, and severe results for any urinalysis parameter will be presented for participants who enrolled prior to Protocol v11.0 in **Table 173** by treatment group, severity at baseline, time point, and maximum severity across all graded chemistry parameters. Proportions of participants with results that are mild, moderate, severe, life-threatening, or result in death for any urinalysis parameter will be presented for participants who enrolled under Protocol v11.0 in **Table 174** by treatment group, severity at baseline, time point, and maximum severity across all graded chemistry parameters.
- Proportions of participants with graded abnormal results will be presented by treatment group, severity at baseline, time point, and severity separately for participants enrolled prior to Protocol v11.0 and for participants enrolled under Protocol v11.0 for urinalysis parameters beginning in **Table 175** through **Table 190**. The proportions of participants with ONR results will be presented by treatment group, severity at baseline, time point, and severity for urinalysis parameters that do not have toxicity grading ranges defined in **Table 191** through **Table 194**.
- Proportions of participants with graded CS urinalysis results post-baseline will be presented by parameter, treatment group, and maximum severity of all CS results post-baseline for participants enrolled prior to Protocol v11.0 in **Table 198** and for participants enrolled under Protocol v11.0 in **Table 199**. The proportions of participants with CS ONR urinalysis results post-baseline will also be presented by parameter, treatment group, and maximum severity of all CS results for parameters that do not have toxicity grading ranges defined in **Table 200** for participants enrolled prior to Protocol v11.0 and in **Table 201** for participants enrolled under Protocol v11.0.

Descriptive statistics for each continuous laboratory parameter and its change from baseline, including mean, SD, median, min, and max, will be presented together for all participants by treatment group and planned time point.

- Descriptive statistics for each continuous chemistry parameter and its change from baseline will be presented by treatment group and planned time point in **Table 104** through **Table 119**.
- Descriptive statistics for each continuous hematology parameter and its change from baseline will be presented by treatment group and planned time point in **Table 146** through **Table 155**.
- Descriptive statistics for each continuous coagulation parameter and its change from baseline will be presented by treatment group and planned time point in **Table 168** through **Table 170**.
- Descriptive statistics for each continuous urinalysis parameter and its change from baseline will be presented by treatment group and planned time point in **Table 195** through **Table 196**.

Mean change from baseline with bars representing  $\pm 1$  SD will also be presented for each continuous laboratory parameter by treatment group and time point in the following figures.

- Mean change from baseline will be presented for continuous chemistry parameters in [Figure 17](#) through [Figure 32](#).
- Mean change from baseline will be presented for continuous hematology parameters in [Figure 33](#) through [Figure 41](#).
- Mean change from baseline will be presented for continuous coagulation parameters in [Figure 42](#) through [Figure 44](#).
- Mean change from baseline will be presented for continuous urinalysis parameters in [Figure 45](#) and [Figure 46](#).

## 9.7. Vital Signs and Physical Evaluations

Vital signs will include systolic blood pressure, diastolic blood pressure, heart rate, respiratory rate, and temperature. Vital signs will be assessed according to the schedule detailed in [Section 4.1](#) and [Table 2](#). Baseline will be defined for vital sign assessments according to the definition given in [Section 3.3](#). Clinical significance for post-baseline vital signs will be determined by the site PI with consideration to persistence, association with clinical symptoms, and impact to participant safety. For participants who screened and enrolled prior to Protocol v11.0, clinically significant vital signs will be determined by a blinded review from the site PI of all vital sign AEs reported. For participants who screened and enrolled with Protocol v11.0, clinically significant vital signs will include all abnormal vital signs results reported as AEs.

Toxicity grading criteria for vital signs results can be found in [Table 5](#) and [Table 6](#) for participants who screened and enrolled prior to Protocol v11.0. Vital signs results post-dosing for participants who screened and enrolled with Protocol v11.0 will be graded according to NCI CTCAE, Version 5.0 – November 2017. The distribution of vital signs results will be presented by severity, treatment group, and time point.

The sort order for vital signs assessments will be as follows: SBP, DBP, heart rate, respiratory rate, and temperature.

- Proportions of participants with mild, moderate, and severe results for any vital sign assessment will be presented for participants who enrolled prior to Protocol v11.0 in [Table 202](#) by treatment group, time point, and maximum severity. Proportions of participants with results that are mild, moderate, severe, life-threatening, or result in death for any vital sign assessment will be presented for participants who enrolled under Protocol v11.0 in [Table 203](#) by treatment group, time point, and maximum severity.
- Proportions of participants with graded abnormal vital signs results will be presented by treatment group, time point, and maximum severity separately for participants enrolled prior to Protocol v11.0 and for participants enrolled under Protocol v11.0 for vital sign parameters beginning in [Table 204](#) through [Table 213](#). Vital sign parameters with separate high and low toxicity ranges will be summarized by maximum severity for both high and low ranges.
- Proportions of participants with clinically significant vital signs results post-baseline will be presented by parameter, treatment group, and maximum severity post-baseline for participants enrolled prior to Protocol v11.0 in [Table 219](#) and for participants enrolled under Protocol v11.0 in [Table 220](#).

Descriptive statistics for each vital sign parameter and its change from baseline, including mean, SD, median, min, and max, will be presented by treatment group and planned time point in **Table 214** through **Table 218**. Mean change from baseline will also be presented with bars representing  $\pm 1$  SD for each vital sign parameter by treatment group and planned time point in **Figure 47** through **Figure 51**.

All vital sign measurements, including height, weight, and BMI, will be listed by treatment group and time point with severity, applicable reference ranges, and change from baseline in **Listing 22**. Unscheduled vital signs measurements will be included in the listing but will otherwise be excluded from tabular and graphical summaries by time point, except when calculating the maximum severity post baseline.

Complete physical examinations and symptom-directed physical examinations will be performed according to the scheduled given in **Section 14** and **Table 2**. All physical examination findings, whether from exams performed at scheduled or unscheduled time points, will be listed in **Listing 23** by treatment group and time point with body system and whether the finding was reported as an AE.

## 9.8.      **Electrocardiograms**

Standard 12-lead ECGs will be performed at Screening (in triplicate), Day 1 prior to dosing, Day 4, final study visit (Day 150), and ET visits. Unscheduled 12-lead ECG measurements will be listed but excluded from tabular and graphical summaries by time point. Individual ECG measurements, overall interpretations, and abnormal findings will be presented in **Listing 24**, **Listing 25**, and **Listing 26**, respectively.

Clinical significance for post-dose ECGs will be determined by the site PI with consideration to persistence, association with clinical symptoms, and impact to participant safety. For all participants, clinically significant ECG parameters will include any results meeting toxicity grading criteria (using **Table 4** for participants who screened and enrolled prior to Protocol v11.0 or NCI CTCAE, Version 5.0 for participants who screened and enrolled with Protocol v11.0) who had an overall ECG interpretation of abnormal, clinically significant.

The sort order for ECG parameters will be as follows: PR interval, QRS duration, QT interval, QTcF correction, RR interval, and ventricular rate.

12-lead standard ECG results will be summarized in the following tables and figures:

- Change in overall interpretations of post-dose 12-lead standard ECG results from baseline will be summarized by treatment group and time point in **Table 221**.
- Descriptive statistics for each ECG parameter and its change from baseline, including mean, SD, median, min, and max, will be presented by treatment group and planned time point in **Table 222**.
- Mean change from baseline of ECG parameters will also be presented with bars representing  $\pm 1$  SD by treatment group and planned time point beginning in **Figure 52** and continuing through **Figure 57**.

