## **3.3 Study Endpoints or Outcome Measures**

### **3.3.1 Primary**

- Occurrence of AEs and SAEs following the start of study product administration through the final visit (Day 150 [ $\pm 7$ ]), or Early Termination (ET).
- The occurrence of clinically significant (CS) changes from baseline in vital signs and clinical safety laboratory values following administration of study product through the final visit (Day 150 [ $\pm 7$ ]), or ET.
- The occurrence of CS changes in ECG parameters post administration of study product through the final visit (Day 150 [ $\pm 7$ ]), or ET.

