#### **3.2. Endpoints**

##### **3.2.1. Primary**

- Occurrence of adverse events (AEs) and serious adverse events (SAEs) following the start of study product administration through the final visit (Day 150 [ $\pm 7$ ]), or Early Termination (ET).
- The occurrence of clinically significant (CS) changes from baseline in vital signs and clinical safety laboratory values following administration of study product through final visit (Day 150 [ $\pm 7$ ]), or ET.
- The occurrence of CS changes in electrocardiogram (ECG) parameters post administration of study product through the final visit (Day 150 [ $\pm 7$ ]), or ET.

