#### **4.5.1. Safety Variables**

The following safety endpoints will be assessed:

- Chemistry (CHEM), Hematology (HEM), Urinalysis (UA), and Coagulation (COAG) clinical laboratory result safety parameters will be collected according to the schedule of study procedures in [Table 2](#). The following parameters will be measured:
  - CHEM parameters: alanine aminotransferase (ALT), aspartate aminotransferase (AST), creatinine, total bilirubin, sodium, potassium, bicarbonate, glucose, blood urea nitrogen

(BUN), calcium, alkaline phosphatase (AP), direct bilirubin, albumin, total protein, estimated glomerular filtration rate (eGFR), and Cystatin-C.

- HEM parameters: hemoglobin (HGB), platelet count, white blood cell (WBC) count, hematocrit (HCT), red blood cell (RBC) count, basophil count, eosinophil count, lymphocyte count, monocyte count, and neutrophil count.
- COAG parameters: activated partial thromboplastin time (APTT), prothrombin time (PT), and international normalized ratio (INR).
- UA parameters: protein, occult blood, ketones, leukocyte esterase, glucose, bilirubin, nitrites, urobilinogen, WBC, and urine RBC.
  - UA will first be performed by urine dipstick testing. If any abnormal value is observed on the urine dipstick test, then urine microscopy will be performed, and the results will supersede those of the dipstick UA.
- Vital signs (VS) parameters will be collected according to the schedule in **Table 2**. The following parameters will be measured:
  - Resting (measured after lying supine for at least 5 minutes) temperature, heart rate, systolic blood pressure (SBP), diastolic blood pressure (DBP), and respiratory rate
- ECG parameters will be collected according to the schedule in **Table 2**. The following parameters will be measured:
  - PR interval, QRS duration, QT interval, QT corrected for heart rate by Fridericia's cube root (QTcF) correction, RR interval, and ventricular rate.
    - Triplicate ECGs with 10-second rhythm strips will be obtained within a 60-minute period prior to dosing and within approximately 15 minutes after dosing is complete, separated by at least 1 minute.
    - Single, standard 12-lead safety ECGs will also be obtained.
    - If any significant changes are observed, triplicate ECG tracings, approximately 2 minutes apart, should be recorded and repeated hourly until cessation of the abnormality. Significant changes are defined as
      - Any significant change in rate or rhythm as determined by the site PI

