## 6. GENERAL STATISTICAL CONSIDERATIONS

### 6.1. General Principles

Unless otherwise specified, continuous variables will be summarized by the following descriptive statistics: the number of participants with non-missing data included in the analysis (n), mean, standard deviation (SD), median, minimum value (min), and maximum value (max). Summary statistics for discrete data will include frequencies and proportions and may include confidence intervals (CIs) for the proportion. When 95% CIs are given for a proportion, exact (Clopper-Pearson) CIs will be used, unless otherwise specified.

All randomized participants will be included in summaries of participant demographics. The Safety Population will be used for summaries of safety endpoints, the PK Population will be used for summaries of PK endpoints, and the Immunogenicity Population or the Pharmacokinetics – Immunogenicity Subset Population will be used for summaries of immunogenicity endpoints. Denominators for clinical, clinical laboratory, VS, and ECG results at planned study time points will be the number of participants in the Safety Population with available results at the specified time point for that parameter. Denominators for the conceptual “Maximum Severity Post Baseline” time point for clinical, clinical laboratory, VS, and ECG results will be the number of participants with an observed result for the parameter obtained post-dose. Unless otherwise specified, denominators for all other safety endpoints will be the number of participants in the Safety Population. All tables will be annotated with the total population size relevant to that table/group, including any missing observations.

The sort order for listings is indicated in the implementation note for each listing shell. The sort order of treatment groups is given in [Section 3](#). The sort order of clinical laboratory tests, VS, and ECG parameters is described in [Section 9](#).

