Diastolic Blood Pressure	All Participants											
	SAR440894 0.3 mg/kg											
	...											
	Placebo											
...	...											

Notes: Participants are counted once per maximum severity among all clinically significant vital signs experienced at any time point post baseline, including unscheduled assessments. N = Number of participants in the Safety Population enrolled under Protocol v11.0 with available results post-baseline.

**Table 221: Summary of Post Dose ECG Change in Overall Interpretations from Baseline by Treatment Group and Time Point - Safety Population**

[Implementation Note: This table will include the following treatment groups: All Participants, SAR440894 0.3 mg/kg, SAR440894 1 mg/kg, SAR440894 3 mg/kg, SAR440894 10 mg/kg, SAR440894 20 mg/kg, Placebo.]

Treatment Group	N	Change from Baseline in ECG Interpretation					
		Normal at Both Times n (%)	Normal to Abnormal, NCS n (%)	Normal to Abnormal, CS n (%)	Abnormal, NCS at Both Times n (%)	Abnormal, NCS to Abnormal, CS n (%)	Abnormal, NCS to Normal n (%)
Day 1							
All Participants	x	x (x)	x (x)	x (x)	x (x)	x (x)	x (x)
SAR440894 0.3 mg/kg	x	x (x)	x (x)	x (x)	x (x)	x (x)	x (x)
...							
Placebo	x (x)	x (x)	x (x)	x (x)	x (x)	x (x)	x (x)
Day 4							
All Participants	x	x (x)	x (x)	x (x)	x (x)	x (x)	x (x)
SAR440894 0.3 mg/kg	x	x (x)	x (x)	x (x)	x (x)	x (x)	x (x)
...							
Placebo	x	x (x)	x (x)	x (x)	x (x)	x (x)	x (x)
Final Visit (Day 150)							
All Participants	x	x (x)	x (x)	x (x)	x (x)	x (x)	x (x)
SAR440894 0.3 mg/kg	x	x (x)	x (x)	x (x)	x (x)	x (x)	x (x)
...							
Placebo	x	x (x)	x (x)	x (x)	x (x)	x (x)	x (x)

Notes: N = Number of participants in the Safety Population with ECG measurements at the time points indicated.  
NCS = Not clinically significant, CS = Clinically significant.

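### No planned table counts each participant once for any clinically significant post-dose ECG change, although that occurrence is a primary endpoint

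*SAP*

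**What the plan says.** Protocol 3.3.1 gives the endpoint as "The occurrence of CS changes in ECG parameters post administration of study product through the final visit" at Day 150, or ET. SAP 3.2.1 repeats it.

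The ECG displays in SAP 9.8 are Table 221, Table 222 and Figures 52 to 57, all by time point. Table 221 is titled "Summary of Post Dose ECG Change in Overall Interpretations from Baseline by Treatment Group and Time Point". Its shell gives participant n (%) for each shift category, two of which end in abnormal-CS, at Day 1, Day 4 and the final visit. On other tracings SAP 9.8 says: "Unscheduled 12-lead ECG measurements will be listed but excluded from tabular and graphical summaries by time point". No exception follows.

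Two further provisions point to a display that is not planned:
- SAP 6.1 sets denominators for a maximum-severity-post-baseline time point and names ECG among the data types: "ECG results will be the number of participants with an observed result for the parameter obtained post-dose".
- SAP 9.8 says that "clinically significant ECG parameters will include any results meeting toxicity grading criteria" where the overall interpretation was also abnormal-CS.

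For vital signs, SAP 9.7 also leaves unscheduled measurements out of by-visit summaries, but "except when calculating the maximum severity post baseline". SAP 9.6 makes the same exception for laboratory results.

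**The concern.** The primary analysis is descriptive (SAP 6.8), so the planned tables are the analysis. An occurrence endpoint over the whole follow-up needs a numerator in which each participant counts once if the event happened at any time. Three visit snapshots do not supply that. They cannot be added together without knowing whether the same people recur, and they contain nothing seen off schedule or at ET.

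At stake is the completeness of one of three primary safety results in a first-in-human trial with small groups, where a single participant changes what a dose row says.

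**Working it through.** The plan attaches no sample size, power or event figure to this endpoint, so there is no stated number to reproduce. The check traces the endpoint to the tables and then sizes the gap.

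**1. The primary safety measures side by side**

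| | Laboratory (SAP 9.6) | Vital signs (SAP 9.7) | ECG (SAP 9.8) |
|---|---|---|---|
| Unscheduled results in by-visit summaries | Excluded | Excluded | Excluded |
| Exception for maximum severity post baseline | Yes | Yes | None |
| Any-time CS table that includes unscheduled results | Tables 120–123, 156–159, 171–172, 198–201 | Tables 219–220 | None |

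The ECG denominator in SAP 6.1 and the definition of CS ECG parameters in SAP 9.8 feed no table.

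**2. Where a CS change can be seen first, and where it is then shown**

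- *Scheduled Day 1, Day 4 or Day 150 tracing:* in Table 221, in that visit's row.
- *Unscheduled tracing:* excluded by rule from Tables 221 and 222. Shown in Listings 24 to 26, and in the treatment-emergent adverse event (TEAE) tables if recorded as an adverse event.
- *ET tracing:* SAP 9.8 names ET as an ECG visit, but neither shell has an ET row. The other routes are the same as for an unscheduled tracing.

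No ECG is scheduled between Day 4 and Day 150: 150 − 4 = 146 days. Unscheduled tracings between Day 1 and Day 4 are also left out. ET tracings are foreseeable, because Protocol 5.2.2 lets one dosed participant per cohort withdraw before Day 112 without replacement.

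**3. Is the adverse event route equivalent?**

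Protocol 7.1 records as an adverse event any CS ECG finding that is new, or changed in severity or frequency, after dosing. Protocol 8.5 requires recording of abnormal ECGs when they come with signs or symptoms. An asymptomatic CS change is thus an adverse event under 7.1 but not clearly so under 8.5. The two passages need to be reconciled. The TEAE tables (42 to 45) are organised by MedDRA term and split by protocol version, so they do not isolate the ECG endpoint.

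**4. Size of the gap**

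Inputs: 6 active participants per dose group, and 2 × 5 = 10 pooled placebo (SAP Table 1). The interval is exact Clopper-Pearson, the SAP 6.1 method. The lower limit is the 2.5% quantile of Beta(x, n − x + 1), and the upper limit is the 97.5% quantile of Beta(x + 1, n − x).

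| x/n | Proportion | 95% CI |
|---|---|---|
| 0/6 | 0% | 0 to 45.9% |
| 1/6 | 16.7% | 0.4 to 64.1% |
| 2/6 | 33.3% | 4.3 to 77.7% |
| 0/10 | 0% | 0 to 30.8% |
| 1/10 | 10.0% | 0.3 to 44.5% |

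Check: for 0/6 the upper limit is 1 − 0.025^(1/6) = 0.459. For 1/6 the lower limit is 1 − 0.975^(1/6) = 0.0042.

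- *Off-schedule case:* one participant in a dose group has a CS change only on an unscheduled tracing. Every Table 221 row reads 0/6, while an any-time count reads 1/6. If the change is seen only at ET, that person also leaves the Day 150 denominator and the row reads 0/5.
- *Cumulation case:* Table 221 shows 1/6 at Day 1 and 1/6 at Day 4. The any-time count is 1/6 if this is one person and 2/6 if it is two, and the table cannot tell which.

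**The case against.** The case against has substance, and most of it limits how far the point reaches.

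- A reader might infer that CS ECG changes are never counted per participant. That is wrong: Table 221 does so at each scheduled visit. Only the cumulative count is missing.
- A reader might infer that off-schedule CS changes appear nowhere. They appear in Listings 24 to 26 and, when recorded as adverse events, in the TEAE tables. The listings give no rate, and the TEAE route has the limits shown above.
- A reader might infer that the tracings that show a problem are the ones dropped, because significant changes trigger triplicate tracings that "should be recorded and repeated hourly until cessation of the abnormality". Those repeats follow a change already observed. If a scheduled tracing showed it, that tracing stays in Table 221. Information is lost only when the first sighting is off schedule or at ET.
- ET tracings are missing from the shells, not excluded by a stated rule. The by-visit laboratory and vital-sign shells have no ET row either, but those measures have any-time tables.
- A reader might infer that a PR or QRS change judged CS would not qualify before v11.0, because SAP Table 4 names only arrhythmia and QTc among ECG items. This does not follow. Table 4 has a catch-all row for other conditions, and Table 221 uses the overall interpretation rather than a grade.
- Off-schedule ECGs may be few. The Schedule of Events marks none under unscheduled visits, and Protocol 6.5 leaves extra procedures to the investigator. This bears on how often the gap matters, but does not close it.

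**Conclusion.** The point holds as a gap in the planned display of a primary endpoint. No table gives the number of participants with any CS ECG change through Day 150 or ET. A change first seen on an unscheduled or ET tracing cannot enter Tables 221 and 222 as written. One such participant in a dose group makes the difference between 0% and 16.7% (0.4 to 64.1).

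That size is an illustration. It assumes one affected participant among 6 with post-dose ECGs. The documents give no expected frequency of CS changes or of off-schedule tracings, so they do not support a claim that the ECG result will be biased by any particular amount. Correction before the analysis is still worthwhile: the endpoint runs to ET, the other safety measures already have the needed table, and SAP 6.1 already holds the denominator.

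**What to change.** Three changes to the SAP:

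1. In SAP 9.8, extend the sentence on unscheduled ECGs with an exception: *except when calculating any post-dose CS result*.
2. Add an any-time post-dose row to Table 221, or a separate table parallel to Tables 219 and 220, by treatment group. Count each participant once if any post-dose ECG (scheduled, unscheduled or ET) changes from baseline to an investigator interpretation of abnormal-CS. Use the SAP 6.1 denominator.
3. State in the table note that unscheduled and ET tracings are included.

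Separately, reconcile Protocol 7.1 and 8.5 on when a CS ECG finding is recorded as an adverse event, or state in the SAP which reading the TEAE tables reflect. Rows for the QTcF limits in Protocol 7.1 are optional: those limits trigger repeat tracings, whereas the endpoint rests on the investigator's judgement of significance.

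The cost of items 1 to 3 is one clause, one row or table with its note, and the programming. All the data are already collected, and these items need no protocol amendment.
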